10.2 Statistical considerations

10.2.1 Sample Size

This trial is powered to detect a clinically significant difference in the number of attacks of wheeze between intervention and control arms. We also have some power to detect differential responsiveness (in terms of the primary outcome) to montelukast in the stratum with ALOX5 promoter polymorphism [5/5], compared with the stratum with the ALOX5 [5/x and x/x]" genotype.

Baseline data on mean (0.76) and standard deviation (1.22) of number of attacks are based on data from the UK General Practitioner Research Database on courses of oral steroids (a proxy for number of episodes). These data follow an overdispersed Poisson distribution. To take account of this we used markov chain Monte Carlo simulation in WinBUGs to estimate sample sizes required: (WinBUGS Version 1.4. 2003 Available from: http://www.mrc-bsu.cam.ac.uk/bugs/welcome.shtml). To detect a 33% drop in attack rate requiring medical attention, with a power of 90% and at a significance level of 5%, and a 6% loss to follow up, we require 1050 children in total. A 33% drop in attack rates equates to an attack rate of 0.51 for the treatment group. The clinical significance of these changes is that approximately four children will need to be treated to prevent one clinically severe attack. A sample size of 1200 gives just over 80% power at the 5% significance level to detect an interaction between treatment and genotype if the effect is a 60% reduction in the [5/x plus x/x] and a 20% reduction in the [5/5] stratum. Assuming a 6% dropout, 1300 children will need to be recruited.

10.2.2 Planned recruitment rate

We plan to recruit 1300 children (participants) over 2 years.

10.3 Statistical Analysis

Poisson regression analyses will be applied to determine influence of allocation on the primary outcome and any differential response between the two strata as described below.

10.4 General considerations

Statistical analysis will be performed by a suitably qualified statistician under the supervision of [name].

10.5 Frequency of Analysis

Safety analyses will be conducted at 6-monthly intervals. Efficacy analyses will be conducted on termination of the trial.

WAIT Trial_ Protocol_v7_24th June 2011

Page 43 of 58

10.6 Analysis of children's baseline characteristics

Following data entry and data cleaning, baseline characteristics including age, sex, and ethnic group, ongoing asthma therapy will be compared between intervention and control groups.

10.7 Analysis of primary endpoints

Initial analyses will be performed according to intention-to-treat for all participants with outcome data. Per protocol efficacy analyses will also be performed, excluding data collected after discontinuation of IMP for those participants who discontinue IMP. We will use Poisson regression with a random effect representing individuals to account for overdispersion. Fixed effects will represent the stratification factor (ALOX5 promoter) and treatment centre. The incident rate ratio (relative risk) and 95% confidence interval will be calculated. Analysis will be conducted in Stata version 10. To test for a differential effect by stratum an interaction between stratum and treatment will be fitted to this model as described in 10.8.1.

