5.4 Treatment procedures

IMP will be presented as white granules administered either directly in the child's mouth, or mixed with a spoonful of cold or room temperature soft food (e.g., applesauce, ice cream, carrots and rice). The white sachet containing the granules should not be opened until ready to use. After opening the sachet, the full dose of granules must be administered within 15 minutes. If mixed with food, the granules must not be stored for future use. The granules are not intended to be dissolved in liquid for administration. However, liquids may be taken by the child subsequent to administration. The granules can be administered without regard to the timing of food ingestion. The dose is 1 sachet per day, started when the child has evidence of a viral cold or has wheeze, and stopped after 10 days. If a child vomits after the administration of the IMP no additional dose is given, and parents record this on the diary chart.

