5.7 Follow-up procedures

Parents will be contacted at the following times post-randomisation:

- **+Two months: Telephone call:** a research nurse or research assistant will telephone the subject to check whether the parent has initiated the IMP, the numbers of days the IMP was used, use of healthcare resources, concomitant medications, procedures, days lost from childcare, and parent days lost from work. Parents will also be asked if their child experienced any adverse events, and these will be recorded if so.
- **+Four months: Telephone call:** a research nurse or research assistant will telephone the parent to check whether the parent has initiated the IMP, the numbers of days the IMP was used, use of healthcare resources, concomitant medications, procedures, days lost from childcare, and parent days lost from work. Parents will also be asked if their child experienced any adverse events, and these will be recorded if so.
- **+Six months: Telephone call:** a research nurse or research assistant will telephone the parent to check whether he/she has initiated the IMP, the numbers of days the IMP was used, use of healthcare resources, concomitant medications, procedures, days lost from childcare, and parent days lost from work. Parents will also be asked if their child experienced any adverse events, and these will be recorded if so.
- **+Eight months: Telephone call:** a research nurse or research assistant will telephone the parent to check whether he/she has initiated the IMP, the numbers of days the IMP was used, use of healthcare resources, concomitant medications, procedures, days lost from childcare, and parent days lost from work. Parents will also be asked if their child experienced any adverse events, and these will be recorded if so.
- **+Ten months: Telephone call:** a research nurse or research assistant will telephone the subject to check whether the parent has initiated the IMP, the numbers of days the IMP was used, use of healthcare resources, concomitant medications, procedures, days lost from childcare, and parent days lost from work. Parents will also be asked if their child experienced any adverse events, and these will be recorded if so.

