6.7 Dose modification/reduction/ delay

Administration of IMP will be discontinued in the following circumstances:

1. If the child is prematurely withdrawn from the study because their parents withdraw consent to participate.

WAIT Trial_ Protocol_v7_24th June 2011

Page 31 of 58

- 2. If an investigator concludes that this course of action is in the child's best interests.
- 3. If a child is prescribed regular daily montelukast by a clinician.

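### The per-protocol rule in 10.7 keeps children who never started the trial drug, so that analysis is diluted by non-use exactly as intention-to-treat is

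*Protocol*

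**What the plan says.** Protocol 10.7 sets the base population first: "Initial analyses will be performed according to intention-to-treat for all participants with outcome data". It then adds a per-protocol analysis with a single criterion: "Per protocol efficacy analyses will also be performed, excluding data collected after discontinuation of IMP for those participants who discontinue IMP". No condition refers to whether a course was ever started or completed.

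Treatment as directed is described in 5.4: one sachet a day, "started when the child has evidence of a viral cold or has wheeze, and stopped after 10 days". Section 6.7 lists three circumstances in which the drug is discontinued: "If the child is prematurely withdrawn from the study because their parents withdraw consent to participate"; "If an investigator concludes that this course of action is in the child's best interests"; and "If a child is prescribed regular daily montelukast by a clinician". Section 5.5 lets a randomisation number be reused when a child takes no dose, but only if the medication was not dispensed. It states no analysis exclusion for a child who takes none.

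The use data exist. At every two-monthly call under 5.7 staff "check whether the parent has initiated the IMP, the numbers of days the IMP was used", and at 12 months parents are asked to return the box with used and unused sachets.

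**The concern.** With a daily medicine, stopping is the usual departure from protocol, and cutting data after discontinuation addresses it. Here the medicine is taken in short parent-started courses, so the main departure is an episode for which no course is begun. The rule does not touch that departure. A child with a dispensed but unopened box counts as per protocol for the whole year.

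The per-protocol analysis is the natural place to look if the trial is null and the question is whether the drug failed or was simply not given. As defined, it would sit close to intention-to-treat whatever the uptake, and could be read as showing no effect even in users without having tested that.

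A second, lesser matter is what the rule removes. A clinician's move to regular montelukast is plausibly prompted by repeated attacks, which are the outcome. If the drug works, more placebo than active children would then lose follow-up.

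**Working it through.** **Inputs.** From 10.2.1: control mean 0.76 attacks, SD 1.22, 33% reduction to 0.51, 90% power, 5% significance, 6% loss, 1050 children for the main comparison and 1300 to be recruited. From 10.7: Poisson regression with a random effect per child. The protocol gives no rate of non-use or of switching to regular montelukast, so those below are assumed ranges.

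**Step 1: the plan's own figure.** The per-protocol analysis has no figure of its own, so I checked the inputs against 1050. Two-sided comparison of means: n per arm = 2 × (1.960 + 1.282)² × 1.22² / 0.25² = 501. Total 1002; 1002 / 0.94 = 1066. Using 0.76 × 0.67 = 0.5092 instead of 0.51 gives 498 per arm, 996 in total and 1060 after loss. Both are within 2% of 1050. The inputs are sound and are not in dispute.

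**Step 2: who the rule keeps.**

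| Child | Treated as 5.4 directs? | Under the rule in 10.7 |
|---|---|---|
| No cold or wheeze, no course | Yes | Kept, 12 months |
| Episodes, box dispensed, no course ever started | No | Kept, 12 months |
| Episodes, only some treated | Partly | Kept, 12 months, unless judged to have discontinued |
| Treated, then put on regular montelukast | Until the switch | Kept up to discontinuation |

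The second row is the defect: a child who never began cannot discontinue.

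**Step 3: dilution.** Let x be the share of attack risk in never-users, for whom the ratio is 1. Observed ratio = (1 − x) × 0.67 + x.

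- x = 0.10: 0.603 + 0.10 = 0.703
- x = 0.20: 0.536 + 0.20 = 0.736
- x = 0.30: 0.469 + 0.30 = 0.769

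Intention-to-treat shows the same values; the stated rule corrects none of the dilution. For scale, with 1300 × 0.94 = 1222 children analysed and the Step 1 method, power falls from 95% with no never-users to 90%, 82% and 71%.

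**Step 4: cutting after a switch.** Dispersion = (1.22² − 0.76) / 0.76² = 1.26. I used gamma-Poisson counts with 300,000 children per arm and a true ratio of 0.67. After each qualifying attack there is a fixed chance of switching, and follow-up ends at the attack that triggers the switch.

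| Switch possible from | Chance per attack | Children cut, active v placebo | Raw counts | Crude rates | Random-effect model with log person-time |
|---|---|---|---|---|---|
| Second attack | 20% | about 3% v 6% | 0.69 | 0.69 | 0.673 |
| Second attack | 50% | about 7% v 12% | 0.71 | 0.70 | 0.668 |
| First attack | 50% | not tabulated | 0.74 | 0.71 | 0.672 |

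Cutting is uneven by arm, and it biases raw counts and crude pooled rates towards 1. It does not bias the random-effect model with person-time, because stopping depends only on recorded attacks and the likelihood conditions on those. In a variant where 25-100% of children stop after their first or second attack, the model with person-time gives 0.67-0.68 and raw counts 0.68-0.79.

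**Step 5: both together.** With 20% never-users plus the Step 4 variant, the ratio is 0.72-0.74 with person-time and 0.75-0.83 without. Person-time deals with the cutting but not with non-use.

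**The case against.** The strongest reply has five parts.

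- **The rule is an ordinary on-treatment rule.** Montelukast granules are a prohibited concomitant therapy (6.6) and starting regular montelukast leads to withdrawal (5.11.1), so ending follow-up there is defensible. This stands. A reader might infer that the months after a switch ought to be kept; the documents do not support that, since it would put prohibited open-label drug into a per-protocol set.
- **Outcome-dependent cutting is harmless under the stated model.** A reader might infer that the cutting biases the result even when follow-up time is used. That is true of crude rates but not of the random-effect model with log person-time (Step 4). Section 10.7 does not mention person-time, but that detail is commonly left to an SAP and its absence is not the point here.
- **The cut is not simply treatment failure.** Of the three circumstances in 6.7, one is consent withdrawal and one is investigator judgement. A child who has attacks and stays on trial drug is not cut. Section 10.7 also does not confine discontinuation to the 6.7 list, so a parent who stops giving the drug might be included. All of this stands, but a parent who never began still escapes the rule.
- **Imperfect initiation is part of the strategy under test, and the non-use rates are invented.** The first is a reason for intention-to-treat to lead, not for labelling never-users as per protocol. The second is right: Step 3 shows a range, not an estimate. Training at visit 2 and two-monthly calls may keep non-use low.
- **Starting one course is not treatment as directed either.** Correct. It removes never-users only, and it also drops children who had no episode and followed the protocol. The set should not be described as estimating full adherence.

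**Conclusion.** The point holds for never-users. The rule in 10.7 has no initiation condition, so the per-protocol analysis carries the same dilution as intention-to-treat: 0.67 becomes 0.70, 0.74 or 0.77 if 10%, 20% or 30% of attack risk is in children never given the drug. It cannot support a claim about effect when the drug is used. The size rests wholly on assumed non-use; the direction and the failure of the rule to correct it do not.

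The cutting limb holds only conditionally. Where stopping depends on recorded attacks alone, the ratio moves to about 0.69-0.71 on raw counts and 0.69-0.70 on crude rates (switch from the second attack), and stays at about 0.67 with log person-time in the individual random-effect model. If stopping also depended on unrecorded severity, these simulations would not cover it.

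A reader might also infer that the trial's main result is compromised. It is not: intention-to-treat is the initial analysis, and the sample size is untouched. This is a correction to a supportive analysis, worth making because it is cheap and bears on how a null result would be read.

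**What to change.** In 10.7:

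1. Restrict the per-protocol set to randomised children who started at least one course of trial drug, identified from the initiation and days-of-use data in the two-monthly calls. The decision to start the first course is made blind and before any exposure, so the arms stay comparable within this set.
2. If data after discontinuation are excluded, label that analysis on-treatment and include log person-time to discontinuation in the random-effect Poisson model.
3. Report courses started and days used by arm, because one started course does not show that later episodes were treated.

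The cost is wording in the protocol or SAP and a little extra analysis of data already collected. The downside is a smaller set: never-users drop out, and so do children who had no episode. Intention-to-treat does not change.

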3.1 Overall Design

Randomised, double-blind, placebo-controlled clinical trial

Schema (Key: V = Visit, T = Telephone call, wk = week, m = month, *= in a subgroup of parents)

	V1		V2	T1	T2	T3	T4	T5	T6	V3*
	-2 wk	-1 wk	0 wk	+2m	+4m	+6m	+8m	+10m	+12m	+12m
Informed consent	Х									
Check eligibility criteria	Χ									
Record baseline clinical and	Х									
demographic data										
Review concomitant	Х		Х	Х	X	X	Х	Х	Χ	Х
medications and need for										
medical attention										
Collect saliva sample for	X									
DNA										
Qualitative assessment of			X							Х
parental views*										
Height, weight of child	X									
Collect urine sample for	Х									
urinary leukotriene										
Collect urine sample for			X In the	X In the subset of children attending ED during an exacerbation –						
urinary leukotriene during			timing t	ning therefore unspecified x						
exacerbation*										
Train parents on use of IMP			X							
and use of inhaled short-										
acting beta-2 agonist										
Establish ALOX5		X								
polymorphism status										
Randomisation		Χ								
Withdraw IMP from pharmacy			Х	X – timing variable, depends on expiry date or date initial						
for initial issue/reissue				supply exhausted						
Supply IMP to parents			Χ							
Adverse event recording			Χ	Χ	Х	Х	Х	Х	Х	Χ

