5.2.3 Screening visit #1 (-2 weeks)

At the screening visit, an investigator, research nurse or research assistant will obtain written informed consent for participation in the trial from parents who are willing to take part in the study. The eligibility of children to participate in the study will then be assessed according to the criteria documented in sections 4.1. and 4.2. The parents of all eligible children will be asked to complete baseline assessments of their child's wheeze status including recording of baseline demographic and clinical data and details of concomitant medications, measurement of weight and height, taking a salivary sample using the Oragene paediatric collection system for extraction of DNA and assessment of leukotriene-associated genes, and obtaining a urine sample for leukotriene analysis. A follow-up appointment will be arranged for the issue of the IMP.

5.2.4 (-1 week)

DNA will be extracted from the salivary sample in the Institute for Cell and Molecular Science, Barts and the London, and children assigned to either ALOX5 promoter polymorphism "5/5", or "[5/x and x/x]" genotype. Extracted DNA will be stored at -70°C for batch analysis of >50 polymorphisms in 10 genes encoding components of the LT biosynthetic pathway and the LT receptors. The local pharmacist will then assign a randomisation number to that child as per section 5.5 of this protocol, and withdraw the corresponding IMP from pharmacy on behalf of that subject.

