10.8.2 Pre-specified sub-group analyses

There are 2 pre-specified subgroups for analysis (other than ALOX5 genotype detailed above):

- Parent-reported history of multi-trigger vs viral episodic wheeze phenotype prior to enrolment
- Basal urinary leukotriene concentration

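### The primary and interaction models name only ALOX5 stratum and centre as fixed effects, which gives up a modest amount of precision available from baseline data the trial already collects

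*Protocol*

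**What the plan says.** Protocol section 10.7 sets out the primary model: "We will use Poisson regression with a random effect representing individuals to account for overdispersion". It then lists the covariates: "Fixed effects will represent the stratification factor (ALOX5 promoter) and treatment centre". Section 10.8.1 tests differential response by adding a treatment-by-stratum term to that main model, so both analyses share one covariate set.

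More baseline information is collected than is used there:

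- Section 5.2.3 provides at screening for "recording of baseline demographic and clinical data and details of concomitant medications".
- The schema in section 3.1 has a row, marked at Visit 1, for review of concomitant "medications and need for" medical attention.
- Section 10.6 uses some of these data descriptively: "baseline characteristics including age, sex, and ethnic group, ongoing asthma therapy will be compared between intervention and control groups".
- Section 10.8.2 names two subgroup variables: "Parent-reported history of multi-trigger vs viral episodic wheeze phenotype prior to enrolment" and "Basal urinary leukotriene concentration". Section 10.1.2 also lists wheeze history and urinary leukotriene for association analyses.

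No section enters any of these variables in the primary or interaction model.

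**The concern.** Children enter between 10 months and 5 years of age, with either episodic viral or multi-trigger wheeze, and some take regular inhaled corticosteroid. It is plausible that these features predict how often a child attends. What they predict stays in the child-level random effect when they are left out, and that widens the interval for the treatment effect.

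The main comparison has power to spare. The interaction has less: section 10.2.1 puts its power only a little above 80% at 1200 children, and it is this test that raises recruitment from 1050 to 1300. Any loss of precision therefore matters most there. Section 10.6 also compares the arms at baseline without saying what follows from an imbalance, so naming covariates in advance would remove a reason for adjustment after the fact.

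**Working it through.** **Inputs from section 10.2.1.** "Baseline data on mean (0.76) and standard deviation (1.22) of number of attacks"; treated rate 0.51; 90% power; 5% significance (taken as two-sided); 6% loss; interaction effect of 60% against 20% reduction at N = 1200. Evaluable children at full recruitment: 1300 × 0.94 = 1222, or 611 per arm.

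**Reproducing the stated sample size.** Two-means formula: n per arm = 2 × (1.960 + 1.282)² × 1.22² / 0.25² ≈ 501. The total is 1002, and 1002/0.94 = 1066, within 2% of the stated 1050. The protocol used simulation with settings it does not give, so this matches its result and not its code. A negative binomial formula gives 815, so 1050 is the more cautious figure.

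**Between-child variance.** k = (1.22² − 0.76)/0.76² = (1.4884 − 0.76)/0.5776 = 1.26.

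**Main effect.** With R the share of between-child variance explained by covariates (assumed; not in the protocol):

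Var(log rate ratio) = [1/0.76 + 1/0.51 + 2k(1 − R)]/611

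At R = 0 the bracket is 1.316 + 1.961 + 2.522 = 5.80, and the between-child term is 2.522/5.80 = 43% of it.

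**Interaction.** Control rate 0.76 in both strata; treated rates 0.304 (variant) and 0.608 (5/5). With variant share p, the variance is [1/0.76 + 1/0.304 + 2k(1 − R)]/(600p) + [1/0.76 + 1/0.608 + 2k(1 − R)]/(600(1 − p)). The target is |ln(0.4/0.8)| = 0.693. The protocol does not state p. At p = 0.25 and R = 0 the variance is 7.127/150 + 5.483/450 = 0.0597 and the SE is 0.244. Power is then Φ(0.693/0.244 − 1.96) = 81%, which agrees with the stated interaction power.

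| R (assumed) | Main-effect variance ratio | SE ratio | 95% half-width (log) | Main-effect power | Interaction power, p = 25% | Interaction power, p = 40% |
|---|---|---|---|---|---|---|
| 0 | 1 | 1 | 0.191 | 98.4% | 81.0% | 90.5% |
| 10% | 0.957 | 0.978 | 0.187 | 98.7% | 82.4% | 91.6% |
| 20% | 0.913 | 0.956 | 0.182 | 99.0% | 83.9% | 92.6% |
| 30% | 0.870 | 0.932 | 0.178 | 99.2% | 85.4% | 93.6% |

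**Other variance scale.** On the two-means scale, main-effect power at 1222 is 94.8% without covariates. The between-child part is 0.7284/1.4884 = 49% of the total variance, so R of 10% to 30% is about 5% to 15% of the total. Power then becomes 95.7% to 97.3%. With quasi-Poisson variance the stated interaction power fits a variant share nearer 35% (82.2%), and the same 5% to 15% would take it to 84.1–87.8%. The negative binomial figures are preferred because the planned model has a child-level random effect.

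**Does the target shift?** Negative binomial simulation (400 trials per scenario, R = 20%, p = 40%) gave log rate ratios of −0.404 unadjusted and −0.401 adjusted, with SE 0.096 and 0.092. The interaction estimate was −0.684 in both models, with SE 0.209 and 0.201 and power 90.7% and 92.5%. The rate ratio is essentially unchanged.

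**The case against.** The strongest reply is that nothing here is in error. The model is pre-specified, reflects the stratified randomisation and allows for overdispersion. It gives a valid, unbiased comparison, and the sample size does not depend on covariate adjustment. All of that stands. A reader might infer that the primary analysis is unsound or underpowered; the protocol does not support either.

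A reader might also turn the variance ratios at R = 20% to 30% into 10% to 15% more children, roughly 115 to 185 of 1222, and call that the cost. The arithmetic follows, but it describes a main effect with power to spare. A rate ratio of 0.67 would have an interval of 0.55–0.81 without covariates and 0.56–0.80 at 20% or 30% explained. No decision would turn on that.

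The assumed R could be too generous. Every child has had at least two attacks, the latest within 3 months, which narrows the spread in recent history. The planning SD comes from oral steroid courses used as a proxy, not from unscheduled attendances.

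It is also tempting to say that every useful predictor is recorded at Visit 1. The schema row on medical attention gives no look-back period or count at baseline, and no section states at which visit wheeze phenotype is recorded. That objection stands and limits the fix.

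Finally, a statistical analysis plan that is not shown may add covariates. However, section 10.7 lists its fixed effects explicitly and does not defer the choice, so such a plan would be extending the stated model.

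**Conclusion.** The point holds as a modest efficiency weakness. For the main effect the gain is a 2% to 7% smaller standard error, of little practical consequence. For the interaction it is about 1 to 4 percentage points of power, from about 81% to 82–85%, and about 1 to 3 points at a 40% variant share, where power already starts near 90%.

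These figures rest on three assumptions: that covariates explain 10% to 30% of between-child variance, the variant share, and that dispersion in the primary outcome resembles that of the steroid-course proxy. The direction is secure if the covariates are prognostic; the size is not established by the protocol. The change is worth making because it costs little and helps the test with the smaller power margin.

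**What to change.** In sections 10.7 and 10.8.1, before unblinding, name a short covariate list for both models: age (continuous), regular inhaled corticosteroid use at baseline (yes/no) and parent-reported wheeze phenotype, in addition to stratum and centre. State a simple rule for missing baseline values so that no child is dropped from the intention-to-treat analysis. Check that the baseline form captures wheeze phenotype. Add prior unscheduled attendances only if the Visit 1 record gives a usable count over a defined period. Report the stratum-and-centre model as a sensitivity analysis.

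The cost is a wording change, a little more analysis work and the handling of a few missing baseline values. The three core covariates need no new data, provided the phenotype item is on the form.
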